9.3 Recording and reporting of SAEs, SARs AND SUSARs

Information about AEs and SAEs will be collected from the time of consent. Information about ARs, SARs and SUSARs will be collected from the time of administration of the vaccine. Information about SAEs will be collected for the duration of the study. Information about AEs will be enquired about at every study visit. AEs (apart from those which could reasonably be expected following vaccination- see section 9.2) will be recorded on the adverse event log for the period of 28 days following administration of the vaccine and medically attended adverse events which occur at any time in the study for the maternal participants will be collected. Medical attendance which is a routine part of antenatal care will not be considered an AE. Unscheduled medical attendances and events which meet the definition of an SAE should be recorded for the mother and infant.

Where a participant withdraws consent for further processing of data, this does not preclude the reporting of SARs and SUSARs which are required to continue being reported according to the protocol for regulatory purposes.

SAEs, SARs and SUSARs must be notified to the Sponsor immediately when the investigator becomes aware of the event (within 24 hours). Refer to JRESSOP0006 and ensure the completed SAE report form JRESDOC0012 is sent to the Sponsor by e-mail to [contact]. All sites will correspond directly with the Sponsor, copying the CI into the correspondence.

We will not require SAE reporting for women being admitted to hospital for delivery, including those women who are admitted for induction of labour and caesarean section and neither instrumental delivery nor caesarean section would be reported as an SAE although the reasons for this may be, for example, if a caesarean section took place because of a significant antepartum haemorrhage the latter would be reported as an SAE although the caesarean section would not. Whether to report complications of delivery as an SAE should be decided at the discretion of the local PI with discussion with the Sponsor and CI as necessary.

For each SAE and SUSAR the following information will be collected:

- full details in medical terms and case description
- event duration (start and end dates, if applicable)
- action taken
- outcome
- seriousness criteria
- causality (i.e. relatedness to trial drug / investigation), in the opinion of the investigator
- whether the event would be considered anticipated.

Any change of condition or other follow-up information should be emailed / faxed to the Sponsor as soon as it is available or at least within 24 hours of the information becoming available. Events will be followed up until the event has resolved or a final outcome has been reached. Once all resulting queries have been resolved, the Sponsor will request the original form should also be posted to the Sponsor and a copy to be retained on site.

The collection of safety data in studies involving vaccination in pregnancy raises specific issues and it is important that the information collected about some outcomes of special interest is collected as consistently as possible (Jones, et al. 2016).

The Global Alignment of Immunization safety Assessment in pregnancy (GAIA) consortium have developed case definitions for a range of outcomes of interest. These should be used for the following events.

- Congenital microcephaly
- Failure to thrive
- Low birth weight
- Neonatal encephalopathy
- Respiratory distress in the newborn
- Small for gestational age
- Antenatal bleeding
- Dysfunctional labour
- Fetal growth restriction
- Gestational diabetes mellitus
- Congenital anomalies
- Neonatal death
- Neonatal infections
- Preterm birth
- Stillbirth

- Hypertensive disorders of pregnancy
- Maternal death
- Non-reassuring fetal status
- Post-partum haemorrhage

More details about these can be found via this link (<http://gaia-consortium.net/outputs/>)

All SAEs assigned by the PI or delegate (or following central review) as both suspected to be related to IMP-treatment and unexpected will be classified as SUSARs and will be subject to expedited reporting to the Medicines and Healthcare Products Regulatory Agency (MHRA). The sponsor will inform the MHRA, the REC and Marketing Authorisation Holder (if not the sponsor) of SUSARs within the required expedited reporting timescales.

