3.4 Primary endpoint/outcome

- SARS-COV-2 IgG-specific antibody concentrations measured on blood samples collected from vaccinated maternal subjects at delivery.
- Occurrence of solicited local and general adverse events (AE) that occur during a 7-day follow-up period after each vaccination (i.e., the day of vaccination and 6 subsequent days)
- Occurrence of unsolicited AEs that occur during a 30-day follow-up period after vaccination (i.e., the day of vaccination and 29 subsequent days)

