3.7 Table of endpoints/outcomes

Objectives	Outcome Measures	Timepoint(s) of evaluation of this outcome measure (if applicable)

Primary (maternal)
 
 To determine whether the immune response, in COVID-19 seronegative participants, to immunisation with COVID-19 vaccines according to “long” dosing intervals is superior to that observed following immunisation according to “short” dosing intervals. 	
 SARS-COV-2 IgG-specific antibody concentrations measured on blood samples collected from vaccinated maternal subjects at delivery. 	
Maternal blood sampling at delivery

 To evaluate the reactogenicity of COVID-19 vaccines, when given as 1- or 2-dose vaccination regimens, in pregnant participants. 	
 Occurrence of solicited local and general adverse events (AE) that occur during a 7-day follow-up period after each vaccination (i.e., the day of vaccination and 6 subsequent days) 	
Diary data entry (solicited AE) from Day 0 to Day 6.

	
 Occurrence of unsolicited AEs that occur during a 30-day follow-up period after vaccination (i.e., the day of vaccination and 29 subsequent days) 	
Diary data entry (unsolicited AE) from Day 0 to Day 29.

Secondary Objectives Maternal
 
 To describe pregnancy outcomes in women who receive COVID-19 vaccine(s) during pregnancy. 	
 Pregnancy outcomes from Visit 1 up to 6 weeks after delivery. These include live birth with congenital anomalies, miscarriage, fetal death/still birth (antepartum or intrapartum), mode of delivery, elective/therapeutic termination. 	
Review at delivery and at 3 days, 14 days, and 42-48 days after delivery.

 To evaluate safety in terms of SAEs and medically attended adverse events (MAAEs) in women who receive COVID-19 vaccines during pregnancy. 	
 Occurrence of serious adverse events (SAEs), AEs leading to study withdrawal, and MAAEs from Visit 1 (Day 0) up to 6 weeks after delivery 	
Notification of SAE / AE / MAAE to site by participant from enrolment to 1 year after delivery / birth.

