8.11 Assessment of compliance with treatment

Solicited and unsolicited AEs will be reported by the participant using an online data capturing system. These data entries will be assessed on a daily basis by the study research team. Reminder notifications to complete these daily entries will be sent to the participants. Any non-compliance with this reporting will be noted and followed up by contacting the participant to prompt them to continue with the diary entries.

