9.2 Operational definitions for (S)AEs

We will not require SAE reporting for women being admitted to hospital for delivery, including those women who are admitted for induction of labour and caesarean section and neither instrumental delivery nor caesarean section would be reported as an SAE although the reasons for this may be, for example, if a caesarean section took place because of a significant antepartum haemorrhage the latter would be reported as an SAE although the caesarean section would not. Whether to report complications of delivery as an SAE should be decided at the discretion of the local PI with discussion with the Sponsor and CI as necessary.

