9.7 Reporting urgent safety measures

If any urgent safety measures are taken the CI/Sponsor shall immediately and in any event no later than 3 days from the date the measures are taken, give written notice to the MHRA and the relevant REC of the measures taken and the circumstances giving rise to those measures.

9.8 The type and duration of the follow-up of participants after adverse reactions.

All vaccinations will be given by trained members of staff who are able to deal with an allergic reaction to the vaccine. All participants will be observed for 30 minutes following vaccine administration to ensure that they remain well. All participants will have access to contact details for the study team which they will be able to use if they have any concerns about adverse events following vaccine administration. These are licensed vaccines in adults so significant adverse reactions are extremely unlikely. All adverse events which occur within the 28 days after vaccine administration will be recorded on the AE log as well as all medically attended AE for the maternal participant which occur at any time during the study. Only events which meet the definition of an SAE should be recorded for the infant.

Any SUSAR will need to be reported to the Sponsor irrespective of how long after vaccine administration the reaction has occurred until resolved.

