11.1 Data collection tools and source document identification

The Chief Investigator will be responsible for all data that accrues from the study.

All study data including participant diary will be recorded directly into an EDC system (REDCap) or onto a paper source document for later entry into EDC if direct entry is not available. This includes safety, laboratory and outcome data. Any additional information that needs recording, but is not relevant for the eCRF (e.g signed consent forms) will be recorded on separate paper source documents. All documents will be stored safely and securely in confidential conditions. The EDC online data is stored on University of Oxford servers.

All participant reported adverse event data (both solicited & unsolicited) will be entered onto electronic diary cards (e-diaries) for a maximum of 28 days following administration of the IMP. The eDiary provides a full audit trail of edits and will be reviewed at time-points as indicated in the schedule of events. Any adverse event continuing beyond the period of the diary will be copied into the eCRF as required for safety review.

The participants will be identified by a unique trial specific number and code in any database. The name and any other identifying detail will NOT be included in any trial data electronic file, with the exception of the electronic diaries, for which consent will be obtained to store the participant email address for quality control purposes. Only site research staff and sponsor data managers have access to view the email address.

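### Protocol sections 9.3 and 9.8 give contradictory rules for the 28-day AE log, and the exception in 9.3 points to a definition that does not exist

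*Protocol*

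**What the plan says.** Three places in the Protocol govern the site AE log.

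- Section 9.3: "AEs (apart from those which could reasonably be expected following vaccination- see section 9.2) will be recorded on the adverse event log", and this applies "for the period of 28 days following administration of the vaccine". The same section says that AEs will be asked about at every study visit.
- Section 9.2, which 9.3 cites for the exception, opens with "We will not require SAE reporting for women being admitted to hospital for delivery". It goes on to induction, caesarean section, instrumental delivery and complications of delivery. It contains nothing else.
- Section 9.8: "All adverse events which occur within the 28 days after vaccine administration will be recorded on the AE log". It carries no exception.

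Four places govern the unsolicited-AE outcome.

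- Section 3.4 makes it a primary outcome: "Occurrence of unsolicited AEs that occur during a 30-day follow-up period after vaccination".
- Section 3.7 names its source: "Diary data entry (unsolicited AE) from Day 0 to Day 29".
- Section 8.11: "Solicited and unsolicited AEs will be reported by the participant using an online data capturing system".
- Section 11.1: "All participant reported adverse event data (both solicited & unsolicited) will be entered onto electronic diary cards (e-diaries) for a maximum of 28 days".

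Section 10.3.3 then tabulates all unsolicited AEs and SAEs by the vaccine schedule received. It mentions diary cards only in connection with solicited reactions. Section 7.4 says that staff delivering the study know which vaccine schedule a participant is on.

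**The concern.** Section 9.3 tells sites to leave a class of events off the log and sends them to another section to learn which events these are. That section does not say. Section 9.8 tells the same sites to leave nothing off. A site that reads 9.3 has to supply its own meaning of expected; a site that reads 9.8 logs everything. The completeness of the log can then differ between sites.

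It could also differ between vaccines. The people applying the filter are not blinded, and a site that turned to product information for guidance would find different sources: section 8.3 refers to the SmPC for the Pfizer, Moderna and AstraZeneca vaccines but to the Investigator Brochure for Novavax. The same symptom might then be logged for one vaccine and omitted for another. An event that was never recorded cannot be restored at the analysis stage.

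**Working it through.** No arithmetic decides this point. The check is to set the passages side by side.

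**1. Do 9.3 and 9.8 conflict?** They concern the same instrument (the AE log), the same participants (vaccinated women) and the same period (28 days after vaccination).

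| | Section 9.3 | Section 9.8 |
|---|---|---|
| Which AEs | all except those expected after vaccination | all |
| Window | 28 days | 28 days |
| Definition of the exception | refers to 9.2 | none needed |

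An event that a site regards as expected must be omitted under 9.3 and recorded under 9.8.

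**2. Is the pointer merely misnumbered?** Section 9.2 concerns delivery admissions and procedures, and SAE reporting rather than AE logging. No other section of the Protocol lists expected post-vaccination events, so a corrected section number would have nothing to point to. The charitable reading is that expected events means the solicited eDiary terms. That reading does not settle the matter from the text either: sections 3.4, 3.7, 10.3.3 and 11.1 refer to solicited events without naming them, and 9.3 does not mention them.

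**3. Does the filter reach the primary unsolicited-AE outcome?** Sections 3.7, 8.11 and 11.1 all route unsolicited AEs through the participant's diary. None of them excludes expected events, and 9.3 gives staff no authority to remove diary entries. By this route the filter does not touch the outcome.

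Three features keep the log from being plainly irrelevant:

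- Section 9.3 has AEs asked about at every visit. An AE reported there but absent from the diary has the log as its stated place, which is where the filter applies.
- Section 10.3.3 limits only solicited reactions to diary cards; its phrase on unsolicited AEs has no stated source.
- The outcome covers Day 0 to Day 29, which is 30 days. The diary lasts at most 28 days. Counting the vaccination day as the first of the 28, it ends on Day 27 and leaves 2 days; counting 28 days after it, it ends on Day 28 and leaves 1 day. The diary as described does not span the whole outcome window. The log, also 28 days, does not either.

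The Protocol therefore does not say whether diary, log or both supply the unsolicited-AE count.

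**4. Can the effect be sized?** That would need the number of AEs elicited at visits and missing from diaries, the share a site would call expected, and the share of sites following 9.3 rather than 9.8. None of these is in the Protocol.

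**The case against.** The strongest reply is that the primary outcome has its own collection route. The participant enters the diary, is blinded to vaccine outside the open-label cohort 4, and is under no instruction to omit expected events. Staff knowledge of the allocation can colour the log but not the diary. This stands. A reader might infer from 9.3 that the primary unsolicited-AE outcome is itself collected under contradictory rules, or that the safety tables are biased. The documents do not support either inference: the contradiction is shown for the log, and its passage into the tables is only possible.

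It can also be said that other routes limit any loss. Section 9.3 collects medically attended AEs in the mother at any time and SAEs throughout, so what could drop out is mainly non-serious, non-attended events of an expected type, which the diary is suited to capture. This also stands, and it limits the consequence.

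A third reply is that expectedness has a standard, because section 9.4 refers to the Reference Safety Information. This carries less weight. That section concerns the assessment of reported events and reactions. Section 9.3 does not cite it for deciding what goes on the log.

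None of these replies reconciles 9.3 with 9.8.

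**Conclusion.** The point holds for the AE log. Sections 9.3 and 9.8 cannot both be followed, and the exception in 9.3 has no content because the section it cites defines nothing of the kind. This is more than a clerical slip: as written, it allows staff who know the allocation to leave events off a safety record under a filter that nobody has defined.

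For the primary unsolicited-AE outcome the conclusion is conditional. If the tables rest on the diary alone, the filter does not affect them. If log entries also feed them, for example AEs elicited at visits, the filter can reduce the counts unevenly by site and perhaps by vaccine. Section 10.3.3 leaves open which applies. Neither the direction nor the size can be derived. A reader might suppose that every event resembling a known reaction is at risk in all of the roughly 800 women planned. That would require the log to be the only source and every site to apply the exception, and the Protocol supports neither assumption.

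**What to change.** Amend section 9.3 by deleting the bracketed exception and its pointer to 9.2, so that it agrees with 9.8 that all AEs in the window are logged. If double recording is to be avoided, the only events allowed off the log should be the solicited terms captured in the eDiary within the 7-day solicited window, listed by name or by reference to the document that lists them.

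State in section 10.3.3 that unsolicited AEs from both the diary and the log enter the unsolicited-AE tables. The 30-day outcome window and the 28-day diary and log windows should be reconciled in the same amendment, since deleting the exception does not resolve that mismatch.

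The cost is a short text change and slightly more AE log entries. No change to the design or sample size is needed.

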9.4 Responsibilities

Principal Investigator (PI):

Checking for AEs and ARs when participants attend for treatment / follow-up.

1. Using medical judgement in assigning seriousness, causality and whether the event/reaction was using the Reference Safety Information approved for the trial.
2. Ensuring that all SAEs are recorded and reported to the sponsor within 24 hours of becoming aware of the event and provide further follow-up information as soon as available. Ensuring that SAEs are chased with Sponsor if a record of receipt is not received within 2 working days of initial reporting.
3. Ensuring that AEs and ARs are recorded and reported to the sponsor in line with the requirements of the protocol.

Chief Investigator (CI) / delegate or independent clinical reviewer:

1. Clinical oversight of the safety of patients participating in the trial, including an ongoing review of the risk / benefit.
2. Using medical judgement in assigning the SAEs seriousness, causality and whether the event was anticipated (in line with the Reference Safety Information) where it has not been possible to obtain local medical assessment.
3. Using medical judgement in assigning whether and event/reaction was anticipated or expectedness in line with the Reference Safety Information.

4. Immediate review of all SUSARs.
5. Review of specific SAEs and SARs in accordance with the trial risk assessment and protocol as detailed in the Trial Monitoring Plan.
6. Assigning Medical Dictionary for Regulatory Activities (MedDRA) or Body System coding to all SAEs and SARs.
7. Preparing the clinical sections and final sign off of the Development Safety Update Report (DSUR).

Sponsor:

1. Central data collection and verification of AEs, ARs, SAEs, SARs and SUSARs according to the trial protocol onto a database.
2. Reporting safety information to the CI, delegate or independent clinical reviewer for the ongoing assessment of the risk / benefit according to the Trial Monitoring Plan.
3. Reporting safety information to the independent oversight committees identified for the trial (Data Monitoring Committee (DMC) and / or Trial Steering Committee (TSC)) according to the Trial Monitoring Plan.
4. Expedited reporting of SUSARs to the Competent Authority (MHRA in UK) and REC within required timelines.
5. Notifying Investigators of SUSARs that occur within the trial.
6. The unblinding of a participant for the purpose of expedited SUSAR reporting [For double blind trials only].
7. Checking for (annually) and notifying PIs of updates to the Reference Safety Information for the trial.
8. Preparing standard tables and other relevant information for the DSUR in collaboration with the CI and ensuring timely submission to the MHRA and REC.

Trial Steering Committee (TSC):

In accordance with the Trial Terms of Reference for the TSC, periodically reviewing safety data and liaising with the DMC regarding safety issues.

Data Monitoring Committee (DMC):

In accordance with the Trial Terms of Reference for the DMC, periodically reviewing overall safety data to determine patterns and trends of events, or to identify safety issues, which would not be apparent on an individual case basis.

9.5 Notification of deaths

All deaths, including deaths deemed unrelated to vaccination will be reported to the Sponsor within 48 hours of the investigator becoming aware of the death.

9.6 Overdose

This study involves administration of vaccines to participants. Women will be asked if they have received the whooping cough vaccination or COVID-19 vaccines previously in their pregnancy and if there is any uncertainty both the handheld notes and GP records will be consulted. It is extremely unlikely that a participant will receive an overdose of trial medication. If this happens, advice should be sought from the local Principal Investigator in discussion, if necessary, with the Chief Investigator.

9.7 Reporting urgent safety measures

If any urgent safety measures are taken the CI/Sponsor shall immediately and in any event no later than 3 days from the date the measures are taken, give written notice to the MHRA and the relevant REC of the measures taken and the circumstances giving rise to those measures.

9.8 The type and duration of the follow-up of participants after adverse reactions.

All vaccinations will be given by trained members of staff who are able to deal with an allergic reaction to the vaccine. All participants will be observed for 30 minutes following vaccine administration to ensure that they remain well. All participants will have access to contact details for the study team which they will be able to use if they have any concerns about adverse events following vaccine administration. These are licensed vaccines in adults so significant adverse reactions are extremely unlikely. All adverse events which occur within the 28 days after vaccine administration will be recorded on the AE log as well as all medically attended AE for the maternal participant which occur at any time during the study. Only events which meet the definition of an SAE should be recorded for the infant.

Any SUSAR will need to be reported to the Sponsor irrespective of how long after vaccine administration the reaction has occurred until resolved.

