3.2 Secondary objectives

Maternal

- To describe pregnancy outcomes in women who receive COVID-19 vaccine(s) during pregnancy.
- To evaluate safety in terms of SAEs and medically attended adverse events (MAAEs) in women who receive COVID-19 vaccines during pregnancy.
- To evaluate safety in terms of AESI (including potential immune-mediated medical conditions (PIMMCs)) relevant to COVID-19, including possible vaccine-enhanced disease, in all women at any time after the first dose of a COVID-19 vaccine.
- To evaluate the immunogenicity of COVID-19 vaccines, when given as 1- or 2-dose vaccination regimens, in serologically negative (to SARS-CoV-2) pregnant participants.
- To evaluate the immunogenicity of COVID-19 vaccines, when given as 1- or 2-dose vaccination regimens, in pregnant participants (regardless of serostatus as baseline).

Infant

- To evaluate the safety of infants born to women vaccinated with COVID-19 vaccine(s) up to 12 months after birth.
- To evaluate the transfer of SARS-CoV-2 specific antibodies from mothers vaccinated with COVID-19 vaccine(s), according to different regimens, to their infants at the time of delivery
- To evaluate the kinetics of SARS-CoV-2 specific maternal antibodies in infants born to mothers vaccinated with COVID-19 vaccine(s), up to 3 months after birth
- To assess the effect of gestational age at vaccination, interval between vaccination and delivery, maternal age, health status, vaccine type and schedule on immune responses and duration of immune responses in vaccinated women and on placental transfer and antibody kinetics in their infants

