3.5 Secondary endpoints/outcomes

Maternal

- Pregnancy outcomes from Visit 1 up to 6 weeks after delivery. These include live birth with congenital anomalies, miscarriage, fetal death/still birth (antepartum or intrapartum), mode of delivery, elective/therapeutic termination.
- Occurrence of serious adverse events (SAEs), AEs leading to study withdrawal, and MAAEs from Visit 1 (Day 0) up to 6 weeks / 6 months after delivery

- AEFI from Visit 1 up to 6 weeks after delivery. These include but are not limited to maternal death, hypertensive disorders of pregnancy (gestational hypertension, pre-eclampsia, pre-eclampsia with severe features including eclampsia), antenatal bleeding (morbidly adherent placenta, placental abruption, caesarean scar pregnancy, uterine rupture), postpartum haemorrhage, fetal growth restriction, gestational diabetes mellitus, non-reassuring fetal status, pathways to preterm birth (premature preterm rupture of membranes, preterm labour, iatrogenic preterm birth), chorioamnionitis, oligohydramnios, polyhydramnios, gestational liver disease (intrahepatic cholestasis of pregnancy, acute fatty liver of pregnancy), maternal sepsis.
- SARS-COV-2 IgG-specific antibody concentrations, (and neutralizing antibody titres and cellular immune responses in subsets) measured on blood samples collected from vaccinated maternal subjects at Day 0 (before vaccination), Day 28-42, Day 56-84, Day 84-112, Day 112-140, at delivery, between 4 weeks and 12 weeks, and at 12 months after delivery

Infant

- From birth through 6 weeks after birth, occurrences of SAEs, AEs leading to study withdrawal, and MAAEs
- Occurrence of neonatal AEs of special interest (up to 6 weeks after birth). These include but are not limited to small for gestational age, low birth weight including very low birth weight, neonatal encephalopathy, congenital microcephaly (postnatally or prenatally diagnosed), congenital anomalies (major external structural defects, internal structural defects, functional defects), neonatal death (in a preterm live birth or in a term live birth), neonatal infections (blood stream infections, meningitis, respiratory infection), respiratory distress in the neonate, preterm birth, failure to thrive, large for gestational age, macrosomia
- Developmental status at 12 months of age

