
 To evaluate the immunogenicity of COVID-19 vaccines, when given as 1- or 2-dose vaccination regimens, in pregnant participants (regardless of serostatus as baseline). 	
 SARS-COV-2 IgG-specific antibody concentrations, (and neutralizing antibody titres and cellular immune responses in subsets) measured on blood samples collected from vaccinated maternal subjects at Day 0 (before vaccination), Day 28-42, Day 56-84, Day 84-112, Day 112-140, at delivery, between 4 weeks and 12 weeks, and at 12 months after delivery 	
Maternal blood sampling at Day 0 (before vaccination), Day 28-42, Day 56-84, Day 84-112, Day 112-140, at delivery, between 4 weeks and 12 weeks, and at 12 months after delivery

Secondary Objectives
 
Infant
 
 To evaluate the safety of infants born to women vaccinated with COVID-19 vaccine(s) up to 12 months after birth. 	
 From birth through 6 weeks after birth, occurrences of SAEs, AEs leading to study withdrawal, and MAAEs. 	
Review of SAEs, AEs leading to study withdrawal, and MAAEs at delivery and at 3 days, 14 days, and 42-48 days after delivery, and at 6 months and 12 months.

	
 Occurrence of neonatal AEs of special interest (up to 6 weeks after birth). These include but are not limited to small for gestational age, low birth weight including very low birth weight, neonatal encephalopathy, congenital microcephaly (postnatally or prenatally diagnosed), congenital anomalies (major external structural defects, internal structural defects, functional defects), neonatal death (in a preterm live birth or in a term live birth), neonatal infections (blood stream infections, meningitis, respiratory infection), respiratory distress in the neonate, preterm birth, failure to thrive, large for gestational age, macrosomia 	
Review of neonatal AESIs at delivery and at 3 days, 14 days, and 42-48 days after delivery, and at 6 months and 12 months.

	
 Developmental status at 12 months of age 	
Perform neurodevelopmental assessment at 12 months of age

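### Section 9.8 limits infant recording to SAEs, contradicting section 9.3 and the infant MAAE, withdrawal and neonatal AESI endpoints; separately, the infant event endpoint stops at 6 weeks under a 12-month objective.

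*Protocol*

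**What the plan says.** **Recording rules.** Section 9.8 first requires AEs within 28 days of vaccination to go on the AE log, together with maternal medically attended AEs at any time. It then says of the infant: "Only events which meet the definition of an SAE should be recorded for the infant". Section 9.3 says: "Unscheduled medical attendances and events which meet the definition of an SAE should be recorded for the mother and infant".

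**Endpoints.** Section 3.5 lists two infant event endpoints: "From birth through 6 weeks after birth, occurrences of SAEs, AEs leading to study withdrawal, and MAAEs", and "Occurrence of neonatal AEs of special interest (up to 6 weeks after birth"). The second comes with a list that includes small and large for gestational age, low birth weight, macrosomia, failure to thrive and respiratory distress.

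**Review plan.** For the first endpoint, section 3.7 plans a "Review of SAEs, AEs leading to study withdrawal, and MAAEs at delivery", repeated at 3 days, 14 days, 42-48 days, 6 months and 12 months. The neonatal AESI row has the same times. In section 7 and Appendix 4, Visits 8 to 12 each carry an SAE/AESI/MAAE check.

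**Time horizon.** The infant safety objective in section 3.2 is "To evaluate the safety of infants born to women vaccinated with COVID-19 vaccine(s) up to 12 months after birth". Under it section 3.5 also places "Developmental status at 12 months of age". Section 9.3 adds: "Information about SAEs will be collected for the duration of the study".

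**The concern.** Sections 9.3 and 9.8 both tell site staff what to write down, and they disagree about the infant. Section 9.8 is the narrower, and it excludes event types that the protocol names as secondary endpoints. If sites differ in which section they follow, the number of non-serious infant events will partly reflect site practice. An analysis plan cannot repair this, because an event that was never recorded may be hard to recover.

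The second matter is the period covered. The objective promises infant safety to 12 months, but the SAE/MAAE endpoint written to answer it stops at 6 weeks. It is therefore unclear whether later infant events belong to the endpoint.

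**Working it through.** Apart from one ratio this is a comparison of text.

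**Step 1. What each rule captures for the infant.** The SAE criteria are in section 9.1: death, threat to life, hospitalisation or its prolongation, lasting or significant disability, congenital anomaly, and other important medical events as a matter of judgement.

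| Infant event | Endpoint in 3.5 | Recorded under 9.3 | Recorded under 9.8 |
|---|---|---|---|
| SAE, including an AESI that is serious | yes | yes | yes |
| Non-serious event with an unscheduled attendance | yes (MAAE) | yes | no |
| Non-serious AE leading to withdrawal, no attendance | yes | not named | no |
| Non-serious listed AESI, no attendance | yes | only through case definitions, for some | no |

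The last row needs care. Section 9.3 requires GAIA case definitions for several neonatal outcomes, among them low birth weight, small for gestational age, failure to thrive and respiratory distress. Large for gestational age and macrosomia are not on that list. Matching 9.8 to 9.3 alone would therefore still leave part of the AESI endpoint without an explicit recording rule. The replacement sentence has to follow 3.5 as well.

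**Step 2. Do the visit checks make up for it?** Partly. They prompt staff to ask about AESIs and MAAEs, but 9.8 governs what is then recorded. Early coverage is also thin:
- Visit 7 (delivery) has an infant examination but no SAE/AESI/MAAE check in the text or in the Appendix 4 grids.
- Visit 8 (days 0-7) is only for cohort 3 and the breast milk sub-study.
- For all other infants the first scheduled check is Visit 9, at days 12-16.

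Section 3.7 nevertheless plans review at delivery and at 3 days. The recording rule therefore matters most in the neonatal period.

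**Step 3. Time horizon of the infant SAE/MAAE endpoint.**
- Objective (3.2): 12 months.
- Endpoint (Trial Summary, 3.5, 3.7): 6 weeks.
- Timepoint column for that endpoint (3.7): delivery to 12 months.

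Six weeks is 6 × 7 = 42 days. Visit 12 is at day 364, and 42 / 364 = 0.115, so the endpoint covers about 12% of planned infant follow-up. This is a share of time, not of data lost: Visits 11 and 12 still check for events.

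**The case against.** The best defence is that one sentence in 9.8 stands against the rest of the protocol. Section 9.3 is the section headed for recording and reporting, and section 12 refers to it as the usual reporting process. Section 9.8 concerns follow-up after adverse reactions, and its sentence comes directly after one about the AE log, so it may have been meant to limit only that log. Section 3.7, the visit checks and the case definitions all point towards capture.

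Much of this stands, and it rules out a stronger reading. A reader might infer that the infant MAAE and AESI endpoints cannot be produced, or that non-serious counts will be zero. The documents do not support that. It would need every site to follow 9.8 and disregard 9.3, 3.7 and the visit schedule. Listed AESIs that are SAEs in any case, such as neonatal death and congenital anomaly, are recorded even under 9.8.

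The defence does not remove the contradiction. The sentence is not confined to the log by its wording, and the sentence before it expressly attaches all-time MAAE recording to the mother.

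A reader might also infer that the 12-month objective has been cut to 6 weeks, and that 9.8 did it. Neither holds. Section 9.8 sets no time limit for infant events; the limit is in the endpoint wording. Developmental status at 12 months is an endpoint under the same objective, and SAEs are collected throughout. A 6-week window for neonatal AESIs is coherent in itself.

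**Conclusion.** The contradiction is real and should be corrected. Section 9.8, read as written, conflicts with section 9.3, with three kinds of infant event named in 3.5, with the review plan in 3.7 and with the visit checks. The supportable harm is incomplete, site-dependent capture of non-serious infant events. It could touch any infant from the roughly 800 planned pregnancies, but its size cannot be calculated: the protocol gives neither infant event rates nor the number of sites that would follow each section. The conclusion assumes that some sites take 9.8 literally.

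Of lesser weight, and independent of 9.8, the infant SAE/MAAE endpoint (6 weeks) disagrees with its own objective and timepoint column (12 months).

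**What to change.** 1. Delete the infant sentence in 9.8. Replace it with a statement that infant SAEs, MAAEs, AEs leading to withdrawal and the neonatal AESIs listed in 3.5 are recorded, and make 9.3 say the same.
2. State how infant events at delivery and in the first days are captured for all infants. Visit 8 cannot serve for this, because it is limited to cohort 3 and the breast milk sub-study.
3. Align the objective, endpoint and timepoint column for infant SAEs and MAAEs in the Trial Summary, 3.2, 3.5 and 3.7. One way is to report the data already checked at 6 and 12 months alongside the 6-week result. The 6-week AESI window may stand, provided its timepoint cell in 3.7 agrees.

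Item 1 is one sentence plus a matching edit in 9.3. Item 3 costs little if the objective and timepoints are brought to the endpoint; extending the endpoint would redefine a secondary endpoint. All changes go through the amendment process in section 13.10. The CRF is not shown, so it should be checked that it holds fields for non-serious infant events. Sites already recruiting should be told which rule applies and asked to review infant events recorded so far.
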